PROTOCOL AND STATISTICAL

ANALYSIS PLAN

Protocol Title:

Patient Experiences with the COVID-19 Vaccination after Breast Cancer Treatment

Principal Investigator:

[name] PhD FASTRO

NCT Number:

NCT04872738

Version Date:

March 17, 2023

PARTNERS HUMAN RESEARCH COMMITTEE PROTOCOL SUMMARY

Answer all questions accurately and completely in order to provide the PHRC with the relevant information to assess the risk-benefit ratio for the study. Do not leave sections blank.

PRINCIPAL/OVERALL INVESTIGATOR

[name] PhD FASTRO

PROTOCOL TITLE

Patient Experiences with the COVID-19 Vaccination after Breast Cancer Treatment

FUNDING

The project was supported by Award Number R01CA139118 ([name]) and Award Number P50CA08393 ([name]) from the National Cancer Institute. The content is solely the responsibility of the authors and does not necessarily represent the official views of the National Cancer Institute or the National Institute of Health. This program is supported by the Adele McKinnon Research Fund for Breast Cancer-Related Lymphedema ([name]) the Olayan-Xefos Family Fund for Breast Cancer Research ([name]), and the Heinz Family Foundation ([name]).

VERSION DATE

04.08.2022

SPECIFIC AIMS

Concisely state the objectives of the study and the hypothesis being tested.

- To elicit patient experiences and side effects associated with the COVID-19 vaccine after breast cancer surgery
 - Hypothesis 1: Patients will choose to receive the vaccine on the arm contralateral to axillary lymph node removal, or in the lower extremity if they have had bilateral axillary lymph node removal
 - Hypothesis 2: Patients with a history of breast cancer will experience axillary lymph node swelling after receiving the COVID-19 vaccine at the same rate as the general population
 - Hypothesis 3: Patients with axillary surgery who develop lymph nodes swelling in the ipsilateral side might be at increased risk of developing lymphedema

- Hypothesis 4: Patients who had a COVID infection prior to receiving the vaccine will experience more vaccine side effects than those who were not infected

BACKGROUND AND SIGNIFICANCE

Provide a brief paragraph summarizing prior experience important for understanding the proposed study and procedures.

Breast Cancer-Related Lymphedema: Overview, Incidence, and Risk Factors

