This is a prospective, longitudinal observational cohort study incorporating patient-reported surveys before and/or after vaccine receipt. Female patients who are ≥ 18 years of age and have a history of breast cancer will be eligible. For the MGH site, patients must have received some breast cancer treatment at MGH or its affiliates and received perometry measurements to measure arm volume to be eligible for this study. Per our MGH lymphedema screening records, there are a minimum of 4,947 patients who will qualify for this study. Based on an anticipated survey response of 20%, we anticipate minimal accrual at MGH to be approximately 989 patients.

Briefly describe study procedures. Include any local site restrictions, for example, “Subjects enrolled at Partners will not participate in the pharmacokinetic portion of the study.” Describe study endpoints.

REDCap was used to develop surveys to be sent electronically to patients. We will use the surveys to elicit patient choices around receiving/not receiving the vaccine, injection site of choice and side effects. Complete versions of all survey involved in this study have been attached to this application, but not all questions will be relevant to each patient. Therefore, branching logic is built into our REDCap database to ensure patients only

have to answer the questions that are relevant to them. For example, a patient who receives a COVID-19 vaccine that only has one dose will not need to fill out symptoms information for their second dose as it is not applicable to them.

For all eligible patients from MGH who use MGB Patient Gateway, they will be sent a recruitment letter via MGB Patient Gateway with a REDCap survey link embedded. We have been working with the Partners eCare team to build this recruitment report.

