The invitation to participate was previously resent a second time after 72 hours with no response, and then a third time at seven days after initial contact (prior to new IRB regulations regarding reminders). An updated version of the recruitment letter was sent with the booster survey once this dose becomes available. The letter includes a new second survey link to questions about the booster vaccine. It is stated in the recruitment letter that this is an updated version of the study which makes the survey more user friendly and includes the booster dose. For this reason, all participants will receive the invitation to participate unless they have specifically asked not to be contacted about our study again. A follow up phone call may be made if we do not hear back in 2 weeks. For patients who do not complete the surveys after consenting to participate (either due to forgetting to finish the surveys or having technical difficulties finding the surveys), the Clinical Research Coordinator will call the participant at the phone number in the EPIC chart to assist in completing all surveys. A telephone script is attached.

Since booster doses of all vaccines are recommended by health officials at differing times, we will contact participants securely through Patient Gateway who have already completed survey(s) about their 1st/2nd doses asking them to complete the booster survey as well. This updated booster letter will include information regarding optional arm measurements as well. This states that we would like participants to make appointments for arm measurements 1-2 weeks before the booster, 7-14 days after the booster, 4-6 weeks after the booster, and 3 months after the booster, +/- 2 weeks. This is an optional component of participation in this study. The letter will be sent through patient gateway. The letter will be sent again to participants who have completed surveys about their 1st/2nd doses in March of 2022 as we anticipate many more responses now as the booster had become more widespread. Depending on response rates, we may reach out by phone, using the attached letter as a script, to help participants complete the booster survey.

98 participants are eligible for our study as well as the CANVAX: Cancer, COVID and Vaccination study (2021P000746). We have been collaborating with the CANVAX team and would like for as many participants as possible of these 98 to complete both studies. In the future, both teams will collaborate

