Additionally, we will reach out to participants through Patient Gateway who have consented to the study and experienced some form of swelling and provide them with contact information if they would like to schedule arm measurements before and/or after receiving the booster vaccination. All participants are aware that arm measurements remain available to them as they have in the past. Language for this letter is attached. We will resend an updated letter to participants who reported lymph node swelling after any of the three doses. The updated language is attached. As has been conducted with the booster arm measurements, parking will be compensated for those coming in for additional appointments outside of regular oncology visits. Depending on response rates, we may also reach out to participants by phone using the attached letter as a script.

An additional survey asking questions about prior SARS-CoV-2 infection will be sent to all participants who have consented to participate through answering questions on any doses of the vaccine. The CANVAX study recently published results that prior infection was associated with higher systemic, but not local, symptoms⁴³. We would like to test this in our population and therefore must collect data on any prior infections to

compare with the data we have on vaccine experiences. The invitation to complete this survey, attached, will be sent securely through patient gateway, and we may reach out by phone depending on response rates at the discretion of the PI. A consent addendum is included in the survey language, attached. No new subjects will be enrolled through this survey.

Participants will be aware (explained in consent fact sheet) that we may review their medical records for the purposes of this study and that we will analyze their survey data in conjunction with their breast cancer treatment information and lymphedema screening data.

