Upon completion of the survey study, we may apply for secondary use of data from our Screening Program to analyze perometry and clinicopathological data for participants who have responded to surveys regarding their COVID-19 vaccinations and who are established participants in our MGH Breast Cancer-Related Lymphedema Screening Program (2008P000540 and 1999P009256). We have applied for and been granted secondary use under Insight number 2021P003414. This program routinely screens patients starting at pre-operative baseline, throughout and beyond treatment at their oncology follow-up visits. Screening consists of perometry measurements, a valid and reliable measure of arm volume used for lymphedema screening[29], as well as a patient-reported outcome measure, the Symptoms Experience Index (SEI), a validated measure of symptoms after breast cancer surgery. Analysis of this data will inform BCRL risk after COVID-19 vaccination versus that from our historical control data.

For studies involving treatment or diagnosis, provide information about standard of care at Partners (e.g., BWH, MGH) and indicate how the study procedures differ from standard care. Provide information on available alternative treatments, procedures, or methods of diagnosis.

Not applicable: this study does not involve treatment or diagnosis.

Describe how risks to subjects are minimized, for example, by using procedures which are consistent with sound research design and which do not unnecessarily expose subjects to risk or by using procedures already being performed on the subject for diagnostic or treatment purposes.

The surveys sent, the main research components of this study, do not present risk to patients. We will protect patients by inviting the majority of the study participants through secure Patient Gateway contact. All surveys will be completed in REDCap and all survey responses will be stored in our secure REDCap database. All patients who are offered to participate in this study are already familiar with the MGH Lymphedema Research Program.

Describe explicitly the methods for ensuring the safety of subjects. Provide objective criteria for removing a subject from the study, for example, objective criteria for worsening disease/lack of improvement and/or unacceptable adverse events. The inclusion of objective drop criteria is especially important in studies designed with placebo control groups.

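### Additional arm-measurement outreach goes only to women who reported swelling, and no plan equalises measurement frequency or separates prompted from routine perometry, which risks detection bias in Hypothesis 3 and, by a second route, against historical controls

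*Combined protocol and SAP*

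**What the plan says.** All references are to the combined protocol and SAP.

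- **Hypothesis 3** (Specific Aims): "Patients with axillary surgery who develop lymph nodes swelling in the ipsilateral side might be at increased risk of developing lymphedema". The exposure is ipsilateral node swelling after axillary surgery, and the outcome is lymphedema.
- **General offer** (Research Design and Methods, booster letter): participants who completed the first/second-dose surveys are asked, whether or not they had swelling, to book arm measurements at four times, one before the booster and three after. On these measurements the protocol says "This is an optional component of participation in this study". The letter is sent again in March 2022. Phone contact using the letter as a script is possible, with the stated aim of completing the booster survey. Parking for the optional booster visit is reimbursed without restriction (Recruitment Procedures, remuneration).
- **Targeted offer** (Research Design and Methods, arm-measurement outreach): an additional contact goes to consented participants who "experienced some form of swelling and provide them with contact information if they would like to schedule arm measurements". Then: "We will resend an updated letter to participants who reported lymph node swelling after any of the three doses". Phone calls may follow, and parking is paid for appointments outside regular oncology visits. The same paragraph says all participants know that measurement remains available to them.
- **Use of the data** (Research Design and Methods, secondary use of screening data): perometry from the screening program, which measures routinely at oncology follow-up, will be analysed for survey respondents. "Analysis of this data will inform BCRL risk after COVID-19 vaccination versus that from our historical control data".
- **Statistical Methods**: models for side effects only. There is no lymphedema definition, no Hypothesis 3 analysis, no method for the historical comparison and no mention of measurement frequency.

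**The concern.** Lymphedema is found by measuring arms, so the chance of finding it rises with the number of measurements. The targeted letters make encouragement to be measured depend on reported swelling, which is close to the Hypothesis 3 exposure. Because attendance is optional, women who are worried or have arm symptoms are plausibly the likelier ones to come. The first targeted contact is not confined to lymph node swelling, so it may also select on early signs of the outcome itself. If these extra measurements enter the analysis unmarked, a swelling-lymphedema association can appear when none exists.

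The historical comparison has a related but distinct problem. Vaccinated women are invited to booster-timed measurements that a routine screening schedule would not contain, so they may be measured more often than the historical controls whatever their swelling status.

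The Background section says that fear of lymphedema is high in these patients and that the results will inform recommendations to them. A spurious association would feed the fear that the study set out to examine.

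**Working it through.** **1. The plan's own figure.** The protocol says "there are a minimum of 4,947 patients who will qualify for this study" and, at 20% survey response, "we anticipate minimal accrual at MGH to be approximately 989 patients". 4,947 x 0.20 = 989.4, which reproduces. No power, effect size or lymphedema threshold is stated.

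**2. Model with no true effect.** Each woman has one routine measurement. A fraction u of women also attend three extra ones.

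- Routine only: r = p x sR + (1-p) x f
- With extra visits: e = p x sE + (1-p) x [1-(1-f)^4]
- Observed risk = u x e + (1-u) x r

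**3. Inputs.**

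- p, the one-year lymphedema risk, comes from the Background's lowest and highest five-year figures at an assumed constant hazard: 1-(1-0.083)^0.2 = 1.7% and 1-(1-0.312)^0.2 = 7.2%.
- Exposed share 16%, borrowed from the Background's dose-2 rate of axillary swelling or tenderness for one vaccine: 0.16 x 989 = 158 women, against 989 - 158 = 831.
- Assumed, not in the documents: routine detection sR = 0.6 to 0.9; detection with extra visits sE = 0.95; false crossing per measurement f = 0 to 2%, independent between measurements; and every uptake u. The 20% uptake used below is unrelated to the 20% survey response.

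**4. Two worked cases at 50% versus 20% uptake.**

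- High end (p = 0.0172, sR = 0.6, f = 0.02): r = 0.0103 + 0.0197 = 0.0300; e = 0.0163 + 0.0763 = 0.0926. Swelling group: 0.5 x 0.0926 + 0.5 x 0.0300 = 0.0613. Others: 0.2 x 0.0926 + 0.8 x 0.0300 = 0.0425. Ratio 1.44.
- Low end (p = 0.0172, sR = 0.9, f = 0): r = 0.01548; e = 0.01634. Groups 0.01591 and 0.01565. Ratio 1.02.

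**5. Hypothesis 3 over all input combinations.** The last column is the chance of a false upward result at two-sided p < 0.05 with 158 versus 831 women. The nominal value is 2.5%.

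| Uptake, swelling vs no swelling | Apparent risk ratio | False upward significance |
|---|---|---|
| 20% vs 20% | 1.00 | 2.5% |
| 30% vs 20% | 1.01-1.15 | about 3-6% |
| 50% vs 20% | 1.02-1.44 | about 3-21% |
| 50% vs 5% | 1.02-1.85 | about 3-42% |

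**6. Historical comparison.** Controls have routine measurement only. The vaccinated cohort's risk is 0.16 x (swelling group) + 0.84 x (others).

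| Extra measurement in the vaccinated cohort | Apparent risk ratio |
|---|---|
| General letter only, 20% in all | 1.01-1.42 |
| General plus targeted, 50% vs 20% | 1.01-1.52 |
| Targeted only, 50% vs 0% | 1.00-1.17 |

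In these scenarios most of the distortion comes from the general booster offer, and the targeted letters add a little.

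**7. Per-woman ratio.** Counting false crossings only, the chance of at least one in k measurements is 1-(1-f)^k. At f = 2% it is 2.0% for one measurement and 4.0%, 5.9% and 7.8% for two, three and four. Over f = 1-3% the ratio to a single measurement runs from 1.97 to 3.94. This compares one woman measured two to four times with one woman measured once. It is not a contrast between the study groups.

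**The case against.** The case on the other side is substantial.

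- **The offer is not exclusive to women with swelling.** The booster letter offers four visits to all dose-1/2 responders, is mailed twice and may be followed by phone, and booster parking is unrestricted. This stands. The imbalance is one further optional stream, not the whole of the outreach. It does not vanish, because the protocol presents that stream as additional and describes no counterpart for women without swelling.
- **Letter recipients are not the Hypothesis 3 exposed group.** The letters are not limited to ipsilateral swelling or to axillary surgery, and Hypothesis 1 expects women to choose the opposite arm or the leg. Some recipients are therefore unexposed, which dilutes the imbalance. This stands.
- **The lymphedema analysis is not specified here.** It is secondary use under a separate approval and may already rest on routine visits. This is possible, but nothing in the supplied text says so.
- **Dropping prompted measurements loses the only ones timed to vaccination.** This stands as a cost and is the reason to keep them in a sensitivity analysis.

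Three stronger readings are tempting. A reader might infer that the comparisons are certain to be biased, but uptake is unknown and equal uptake gives 1.00 for Hypothesis 3. A reader might infer that the targeted letters push Hypothesis 3 toward a vaccine effect, but that hypothesis contrasts swelling with no swelling, and only the historical comparison speaks to vaccination. A reader might also take the two- to fourfold per-woman ratio as the size of the bias. That would require every woman with swelling to attend extra visits and no other woman to do so, and it leaves out true cases.

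**Conclusion.** The concern holds as a risk of detection bias that comes from a stated outreach rule and has no described safeguard. For Hypothesis 3 the expected direction is toward a swelling-lymphedema association. For the historical comparison it is upward for the vaccinated cohort, and the general booster-timed measurement is the larger source.

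The size cannot be fixed from the documents. Under the assumptions above it runs from negligible (about 1.0 when routine screening finds nearly all cases with no false crossings, or when uptake is similar) to material (about 1.4 at 50% versus 20% uptake, and up to about 1.85 at 50% versus 5%). These figures rest on assumed uptake, detection and false-crossing rates and on a constant hazard. They also treat all swelling reporters as exposed, which overstates the contrast for Hypothesis 3 as worded. The documents do not support a firm statement that either result will be biased. They do support acting before the lymphedema data are analysed.

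**What to change.** 1. Flag each perometry record as routine (taken at a scheduled oncology follow-up visit) or study-prompted (letter, call or booster schedule). The protocol already singles out appointments outside regular oncology visits for parking, so the flag should be largely recoverable.
2. Base the historical comparison on routine oncology-visit perometry.
3. For Hypothesis 3, make routine-visit perometry the main comparison, and show the result with prompted measurements included as a sensitivity analysis.
4. Report the number of measurements per woman by swelling status, so that any remaining imbalance is visible.
5. If outreach is still open, send the additional measurement letter to all consented participants regardless of swelling. This helps Hypothesis 3, to the extent that uptake becomes similar. It does not help the historical comparison: at 20% uptake in everyone the apparent ratio there is still 1.01-1.42.

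Steps 1 to 4 cost a data flag, a few sentences of analysis plan, and fewer measurements in the main comparison, especially those timed to vaccination. Step 5 costs some Patient Gateway messages and parking passes. Steps 1 to 4 work even if outreach has closed.

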on how best to share our data (perhaps by applying for a data use agreement). Therefore, we will send an additional letter through Patient Gateway to these participants explaining why we would specifically appreciate their participation in the study, signed by the CANVAX PI. These participants have not opted out of being contacted for future research. The Lymphedema Research Program Clinical Research Coordinators are listed as Research Assistants on the CANVAX protocol. If a CANVAX patient is seen in the Breast Cancer Center for routine follow ups or arm measurements, CRCs will offer to have the patient fill out the survey during the visit. Depending on response rate from the Patient Gateway letter, CRCs may also call these patients (a script is attached) unless they decline to participate.

If the participant consents, they will immediately begin a survey asking for information about their first dose and symptoms and second dose and symptoms, if applicable. For participants who have had all doses of their respective vaccines, their participation is complete after responding to a survey about all applicable doses. For participants who have had one dose of their vaccine and plan to have a second, they will fill out the expected date of their second dose and told that the invitation will be resent on that date via Patient Gateway for them to fill out a second survey on that dose. A second link will be available in the recruitment letter directing participants to fill out experiences with the booster dose of the vaccine if they receive it. Copies of both surveys (first/second dose experience and booster dose experience) are attached.

[figure not shown]

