- For participants who are eligible for our study (MGH patients ≥ 18 , female, treated for breast cancer at MGH, have been measured with perometry for BCRL) who also participated in the CANVAX: Cancer, COVID and Vaccination study (2021P000746), the CRC will send an additional letter through Patient Gateway to describe the crossover between the two studies. If a CANVAX patient is seen in the Breast Cancer Center for routine follow ups or arm measurements, CRCs will offer to have the patient fill out the survey during the visit.

Provide details of remuneration, when applicable. Even when subjects may derive medical benefit from participation, it is often the case that extra hospital visits, meals at the hospital, parking fees or other inconveniences will result in additional out-of-pocket expenses related to study participation. Investigators may wish to consider providing reimbursement for such expenses when funding is available

Parking fees will be reimbursed for the optional visit for arm measurements before/after receiving the booster vaccination. Participants will be given a parking pass for a 0-4 hour visit.

For guidance, refer to the following Partners policies:

Recruitment of Research Subjects

<https://www.partners.org/Assets/Documents/Medical-Research/ClinicalResearch/Recruitment-Of-Research-Subjects.pdf>

Guidelines for Advertisements for Recruiting Subjects

<https://www.partners.org/Assets/Documents/Medical-Research/ClinicalResearch/Guidelines-for-Advertisements.pdf>

Remuneration for Research Subjects

<https://www.partners.org/Assets/Documents/Medical-Research/Clinical-Research/Remuneration-for-Research-Subjects.pdf>

CONSENT PROCEDURES

Explain in detail how, when, where, and by whom consent is obtained, and the timing of consent (i.e., how long subjects will be given to consider participation). For most studies involving more than minimal risk and all studies involving investigational drugs/devices, a licensed physician investigator must obtain informed consent. When subjects are to be enrolled from among the investigators' own patients, describe how the potential for coercion will be avoided.

Although this is a minimal risk study, we will ask patients to consent (yes/no) via the initial REDCap survey. There are multiple ways a participant can be recruited to the study, all study patients will first fill out a consent survey that includes the language below.

Are you interested in taking part in this study?

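### Hypothesis 4 tests a published CANVAX finding, but up to 98 specially recruited CANVAX participants are not separated in the analysis, so the test may not be fully independent of CANVAX

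*Combined protocol and SAP*

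**What the plan says.** Hypothesis 4, under Specific Aims, reads: "Patients who had a COVID infection prior to receiving the vaccine will experience more vaccine side effects than those who were not infected".

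The data for it come from a later survey on prior infection, described under Research Design and Methods. The stated reason for that survey is: "The CANVAX study recently published results that prior infection was associated with higher systemic, but not local, symptoms". The protocol continues: "We would like to test this in our population". The survey goes to everyone who has already consented, with no exception for CANVAX participants.

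The same section states that "98 participants are eligible for our study as well as the CANVAX: Cancer, COVID and Vaccination study", and that the team "would like for as many participants as possible of these 98 to complete both studies". To that end, "we will send an additional letter through Patient Gateway to these participants explaining why we would specifically appreciate their participation in the study". The letter is signed by the CANVAX principal investigator. Coordinators may also offer the survey in clinic and may telephone. Recruitment Procedures describes this group as women who took part in CANVAX.

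Statistical Methods lists age, BMI, surgery type, axillary surgery, radiation and chemotherapy as predictors. It mentions neither CANVAX membership nor prior infection.

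**The concern.** A finding tested partly in the people who gave rise to it is not tested independently. A woman who was infected and then reacted strongly to a given dose would tend to report that in both studies. If chance put an excess of such women into CANVAX, the shared women would carry part of that excess into this study. It would count once in raising the hypothesis and again in supporting it.

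The overlap here is sought, not incidental: the extra letter, clinic offers and calls aim to bring in as many of the 98 as possible. What is at stake is the weight a reader can give to agreement between the two studies. The estimate in this cohort, taken on its own, is not invalidated.

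**Working it through.** **Inputs from the protocol (Research Design and Methods).** Eligible pool 4,947; anticipated response 20%; anticipated accrual about 989; women eligible for both studies 98.

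**Input not in the documents.** The size of the CANVAX analysis, Nc. I assume 300, 500 and 1,000 to show the range.

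**Step 1: reproduce the plan's figure.** 4,947 × 0.20 = 989.4, which agrees with about 989.

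**Step 2: share of the sample that could be CANVAX participants.**
- All 98 join: 98/989 = 9.9%.
- The general 20% response applies to them: 98 × 0.20 = 19.6, about 20; 20/989 = 2.0%.

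**Step 3: effect on false confirmation.** Statistical Methods uses p < 0.05 and does not state sidedness. I take it as two-sided, so the chance of a significant result in one given direction is 2.5% when there is no effect. If m women are in both analyses and contribute identically to each, the two test statistics have correlation

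ρ = m / √(989 × Nc).

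The quantity wanted is P(Z > 1.96 here, given Z > 1.96 in CANVAX) for a standard bivariate normal pair with correlation ρ and no true effect. With no overlap it is 2.5%.

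| Assumed Nc | ρ, m = 98 | Rate, m = 98 | ρ, m = 20 | Rate, m = 20 |
|---|---|---|---|---|
| 300 | 0.180 | 5.9% | 0.037 | 3.0% |
| 500 | 0.139 | 5.0% | 0.028 | 2.9% |
| 1,000 | 0.099 | 4.1% | 0.020 | 2.8% |

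For example, at m = 98 and Nc = 300, ρ = 98/√(989 × 300) = 98/544.7 = 0.180.

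**Step 4: two sensitivities.**
- Weaker agreement between the two sets of reports. Halving ρ at m = 98 gives 4.0%, 3.6% and 3.2%.
- A smaller denominator. If only half of the 989 answer the later infection survey but all 98 do, the share is 98/494.5 = 19.8% and the rates are 8.0%, 6.4% and 5.0%. This is a ceiling scenario; the protocol gives no response rate for that survey.

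**Step 5: cost of an estimate without these women.** Interval width scales as 1/√n.
- Without 98: √(989/891) = 1.054, about 5% wider.
- Without 20: √(989/969) = 1.010, about 1% wider.

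Both assume that prior infections are no more common among these women than among the rest.

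**The case against.** A reader might infer that these are the women who produced the CANVAX result. The documents do not show that. They describe the 98 as eligible for both studies and as having taken part in CANVAX. They do not place any of them in the published analysis, and do not say how many had a prior infection or how many enrolled here. This stands, and it is why the point is worded as a possibility.

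The protocol also never claims an independent replication. It speaks of testing the finding in its own population, and it discloses the overlap and the collaboration openly. That stands too: the problem lies in a conclusion that might be drawn later, not in a claim already made.

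Side effects and infection history are collected afresh by this study's own surveys, booster doses are included, and data sharing with CANVAX is only a future possibility. So women might be reused, but CANVAX data would not be. Different questions, recall and doses weaken the correlation, as the halved-ρ figures show. They do not remove it, since the same woman may be recalling the same reaction.

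At the stated 20% response the inflation is only 0.3 to 0.5 percentage points. That is correct, although the extra recruitment is meant to raise response in exactly this group.

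Finally, Statistical Methods contains no prior-infection term at all, which is a more basic gap. It does not answer this point: when the Hypothesis 4 model is written, the overlap still needs a rule.

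**Conclusion.** The point holds in a limited form. The survey was added to test a CANVAX finding, CANVAX participants are deliberately recruited into the sample, and no analysis rule separates them. The test as written is therefore not assured to be independent of CANVAX.

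The size is small to moderate. The upper range of 4.1–5.9% against 2.5% requires all 98 to join, all to have been in the published analysis, and the same reports in both studies, with 989 women analysed here and CANVAX size assumed at 300 to 1,000. At about 20 women, with the other assumptions unchanged, it is 2.8–3.0%. The figure could be larger if few women answer the infection survey or if prior infections cluster among the 98; the documents quantify neither.

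The material does not support calling the test invalid, or insisting that the primary analysis exclude these women.

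**What to change.** 1. Add a CANVAX-membership flag to the analysis dataset. The team has already identified the 98.
2. Report how many of them joined, and how many were in the published CANVAX analysis.
3. When the Hypothesis 4 model is written into Statistical Methods, present the prior-infection estimate with and without CANVAX participants.
4. State that any claim that the CANVAX finding is confirmed rests on the estimate without them. The estimate with them can still describe this cohort.

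The cost is one variable, a few lines of text and a membership check with the CANVAX team, with whom the protocol already describes a collaboration. No new patient data are needed. The estimate without these women has an interval about 1% (20 women) to 5% (98 women) wider, and wider still if prior infections are concentrated among them. The number of previously infected women in each group should therefore be reported alongside.
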